Cognitive Processing Therapy (CPT): CPT is a manualized, 12-session 1:1 cognitive therapy that has been designed for patients with PTSD [76]. In this study the sessions will be conducted weekly. The stated goal of CPT is "to assist the client in refraining from assimilating (distorting the event to fit prior beliefs) and in accommodating schemas to the new information without over-accommodating".[77] CPT uses Socratic questioning targeting distorted cognitions such as self-blame, hindsight bias, and other guilt cognitions. CPT is focused on the cognitive components of the therapy without exposure. Therapy will be provided by psychologists who either have been or will be trained in conventional CPT through the VA rollout initiative. [[name] will be responsible for coordinating therapy and therapists will have weekly case consultation/supervision from a qualified CPT consultant ([name], who is a national CPT trainer and supervisor).]

Individual Drug Counseling (IDC): IDC will serve as the control group. The current standard of treatment for individuals entering buprenorphine maintenance is to do drug counseling. In most VA settings, including VA Connecticut Healthcare System, psychiatric symptoms (such as PTSD) are evaluated but psychiatric treatment is often deferred until the individual demonstrates a commitment to treatment and demonstrates abstinence. Standard counseling is the primary means to achieve these goals. IDC uses a semi-structured, time-limited addictions-counseling model in a 1:1 setting. The main focus is on helping individuals achieve and maintain abstinence by encouraging behavioral changes, such as avoiding triggers, structuring one's life, and engaging in healthy behaviors (e.g., exercise). The IDC manual provides an organized, concise version of what is currently practiced by most addiction counselors. In operationalizing this approach, the developers drew from their own clinical experience and that of expert drug counselors in the field. The approach is consistent with the 12-step approach that regards recovery as a gradual process, and participation in self-help groups such as Alcoholics Anonymous or Narcotics Anonymous is strongly encouraged. IDC will be conducted by study personnel and supervised by [name] on a weekly basis.[78]

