Initial certification for CPT and IDC will be defined as at least adequate or average adherence and competence ratings on the respective CPT and IDC consistent techniques on six consecutive practice sessions. After certification, the therapists will begin seeing participants in the trial. The CPT and IDC supervisors will rate one audio recorded session each week, rotating among study therapists, and discuss feedback in weekly supervision. If this ongoing review determines that a therapist drifts below the initial certification level, then the therapist will be provided additional supervision and training to assure adequate delivery of their assigned treatment.

Fidelity to ratings:

BUP CPT

Page | Page 12 of 24

v. 4/12/2022

To assure the study therapies are delivered in a manner consistent with manual guidelines, all CPT and IDC sessions will be audio recorded* and selected sessions (3 randomly selected sessions from each participant) will be evaluated by raters, who are blind to type of treatment received, using the Yale Adherence and Competence Scale (YACS) rating system developed for assessing therapist adherence and competence in previous trials.[79-81] The YACS consists of a series of Likert-type items utilizing key unique components of specific therapies (e.g., Cognitive Behavioral Therapy, Motivational Interviewing, CPT, Twelve Step Facilitation, contingency management, clinical management) as well as a series of scales utilizing common factors in general drug counseling (e.g., assessment of substance use and functioning, facilitative conditions). For each item, raters are asked to rate the degree to which the therapist used that particular intervention in the session (adherence), as well as how skillfully the therapist implemented the intervention (skillfulness). The YACS measure used in our proposed study will focus on items specific to CPT and IDC, allowing for a test of discrimination between the delivery of the two distinct treatments. The YACS has very good psychometric properties, with coefficient alpha for the treatment scales in the .80-.95 range, indicating a high degree of internal consistency, and ICC's (intraclass correlation coefficients) for the adherence and competence scales ranging from .75 to .90. [name] has extensive experience training YACS raters to perform very reliable session process ratings.

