Subject Payment. All participants will be compensated for their participation. Participants will be paid \$30 for the initial screening/baseline assessment. They will be compensated \$30 for each medication visit (x7), and \$45 for follow up visits. There will be no payment for therapy sessions. Individuals can receive up to a total of \$330 if attending all scheduled treatment and visits. Payment will be made through electronic funds transfer (EFT). Participants will need to provide us with your banking information by completing a special payment form. Alternatively, if participants do not have a bank account, a check will be mailed to them instead. This check(s) will be mailed to the address they provide us with. Patients may choose to receive gift certificates issued to them for use at the VCS canteen (retail store) or VCS cafeteria here at the VACHS in lieu of EFT/check payment. If a patient chooses to receive payment by gift certificate they will be paid for the telemedicine/telehealth visits they participated in at their next in-person visit (e.g. if they complete weeks 2 and 3 by telephone they will receive gift certificates for weeks 2, 3, and 4 at the week 4 visit). Study payments are subject to withholding for outstanding federal debts (i.e., defaulted student loans, interstate child support, back taxes etc) without notification.

Power analysis: The sample size calculation for our primary hypothesis (change in PTSD symptoms) was based on findings from one of the largest and most comprehensive meta-analysis reports on PTSD treatment to date.[36] The report evaluated N=112 studies and reported on 137 comparisons, using validated PTSD symptom measures. The meta-analysis reported that the *effect sizes* for psychotherapy when contrasted with a control group were consistently large and averaged $g=1.14$. Three studies administered CPT specifically and the overall effect size for those was large and averaged $g=1.69$. For this study we conservatively are basing our calculations on a moderate effect size by Cohen's definition.[95] For the First and Second Primary aim we estimate that with 60 subjects randomized to each group we have 80% power to detect a medium effect size ($f=0.25$) at two-sided alpha level of 0.05, and assuming 25% dropout we will recruit a total of N=160.]

Data Analysis:

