Study data will be collected and managed using REDCap electronic data capture tools hosted at VA CT Healthcare System. REDCap (Research Electronic Data Capture) is a secure, web-based application designed to support data capture for research studies, providing 1) an intuitive interface for validated data entry; 2) audit trails for tracking data manipulation and export procedures; 3) automated export procedures for seamless data downloads to common statistical packages; and 4) procedures for importing data from external sources.

Descriptive statistics and graphs will be used to summarize the data on all randomized subjects. All continuous variables will be examined for adherence to the normal distribution using normal probability plots and Shapiro-Wilk tests. Transformations will be applied if needed. If normality is not satisfied and transformations do not help with achieving normality alternative analytic strategies will be considered such as generalized estimating equations (GEE) or nonparametric methods for repeated measures analysis. Baseline demographic and clinical characteristics for the two randomized groups (e.g., age, gender, severity of PTSD, and opiate use) will be compared using chi-square tests for categorical variables and t-tests or nonparametric tests for continuous variables. If there are baseline differences between study treatment groups, these variables will be used as covariates in the mixed-effects models analyses described below. Drop outs and completers will also be compared on baseline characteristics using the same approach. Between group differences in treatment retention, medication compliance and frequency of the occurrence of side effect symptoms across the treatment period will also be assessed. Residual plots and other diagnostics will be used to assess model assumptions.

The primary analyses will be intent-to-treat but sensitivity analyses on completers and non-completers will also be performed. All statistical testing will be at a two-tailed alpha level of 0.05. *Adjustments for multiple comparisons will be conducted among measures in specific domains. In the case of PTSD symptoms (use of 2 measures, PCL-5 and CAPS-5) and opiate use (use of TLFB and urine toxicology) the level of significance will be adjusted to 0.025.*

Primary and Secondary Hypotheses:

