For the primary and secondary hypotheses, we will use mixed effects models to assess changes in PTSD symptoms and opiate use over time. Treatments will be used as between-subject factors and time (in weeks) will be used as a within-subject factor. The primary outcome variables will be PTSD symptoms as measured by generated from the PCL-5 and CAPS scales. The secondary outcome variables will be frequency of opiate use generated from the TLFB and confirmed with urine toxicology results each medication visit (weeks 1-4, 6, 8, 12) and follow-up. The use of the mixed-effects models approach for the analysis of our longitudinal data has several specific advantages. Unlike traditional repeated measures analyses, mixed effects models allow for different numbers of observations per subject, use all available data on each subject and are unaffected by randomly missing data. They also provide flexibility in modeling the correlation structure of the data.[96]

Primary Aim 1. We hypothesize that CPT will significantly reduce PTSD symptoms compared to IDC in Veterans and civilians with PTSD and comorbid OUD maintained on buprenorphine.

This hypothesis will be tested by the interaction of treatment (CPT vs. IDC), and time in the mixed model specified above. Significantly greater decrease in PTSD symptoms in the CPT group will be considered supportive of the hypothesis.

Secondary Aim 1. We hypothesize that CPT will significantly reduce opioid use compared to IDC in Veterans and civilians with PTSD and comorbid OUD maintained on buprenorphine.

This hypothesis will be tested by the same approach as described in primary aim 1 but with frequency of opioid use as the dependent measure.

Exploratory Hypothesis:

We hypothesize that CPT will significantly improve retention (days in treatment) compared to IDC in Veterans and civilians with PTSD and comorbid OUD maintained on buprenorphine.

This hypothesis will be tested using ANOVA or nonparametric equivalent comparing the two treatment groups (CPT vs. IDC).

We hypothesize that CPT will significantly improve psychosocial functioning (measured by the VR-12 survey) compared to standard counseling in Veterans and civilians with PTSD and comorbid OUD maintained on buprenorphine.

This hypothesis will be tested by the interaction of treatment (CPT vs. IDC) and time.

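### The primary treatment-by-time test has no therapist term, so if therapists differ in how much their patients change, its standard error is too small and its type I error exceeds nominal

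*Combined protocol and SAP*

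**What the plan says.** All references are to section 6, Research Plan, of the combined protocol and SAP.

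- **Who delivers CPT** (Cognitive Processing Therapy paragraph): "Therapy will be provided by psychologists who either have been or will be trained in conventional CPT through the VA rollout initiative".
- **Who delivers IDC** (Individual Drug Counseling paragraph): "IDC will be conducted by study personnel". The Methods overview calls them research staff, while item c) under Potential Risks says a licensed provider.
- **More than one therapist, tied to one treatment** (certification paragraph): "The CPT and IDC supervisors will rate one audio recorded session each week, rotating among study therapists". Therapists are certified on the techniques of their own therapy, and one who drifts is retrained on the treatment assigned to them. No sentence says that nobody delivers both.
- **The model** (Primary and Secondary Hypotheses): "Treatments will be used as between-subject factors and time (in weeks) will be used as a within-subject factor". Primary Aim 1 is tested by the treatment-by-time interaction. Data Analysis adds covariates where the arms differ at baseline. No therapist effect, clustered variance or therapist sensitivity analysis is mentioned.
- **Sample size** (Power analysis): "with 60 subjects randomized to each group we have 80% power", for a medium effect (f = 0.25) "at two-sided alpha level of 0.05", with no design effect. For the two PTSD measures, Data Analysis says "the level of significance will be adjusted to 0.025".

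**The concern.** Both treatments are one-to-one talking therapies, so each patient's active treatment comes through one therapist. Patients of a therapist who gets better than average results will tend to improve together. When therapists are nested within arm, the average therapist difference between the arms becomes part of the estimated treatment effect. A model that treats patients as independent does not count the uncertainty in that part. Repeated measures within patient do not help, because the missing correlation is between patients.

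There is a second possible route to the same correlation. The note to Table 1 lets the treating therapist hand out and collect the weekly self-assessments, and the PCL-5, a primary measure, is a self-report scale collected during treatment.

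At stake is whether a significant interaction can be read as an effect of CPT, or could come from having a few stronger or weaker therapists in one arm.

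**Working it through.** **Inputs from the documents.** 60 per arm, f = 0.25 (d = 2f = 0.5 for two groups), two-sided alpha 0.05 in Power analysis and 0.025 per PTSD measure in Data Analysis, 25% dropout.

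**Assumed, because the documents are silent.** ICC of change between patients of one therapist: 0 to 0.10. Therapists per arm k: 3 to 10. Caseloads are equal, m = 60/k. A two-group comparison of change stands in for the treatment-by-time test.

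**Step 1: the plan's own figure.** The expected z is 0.5/√(2/60) = 2.739. Power at 0.05 is Φ(2.739 − 1.960) = 78.2% (77.5% with a t-test), close to the stated 80%. Recruitment is 120/0.75 = 160. The plan's figure is thus approximately reproduced with independent patients.

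**Step 2: error of the unadjusted test.** Design effect DE = 1 + (m − 1) × ICC. The standard error is too small by √DE. The true two-sided error is 2 × [1 − Φ(z/√DE)], with z = 1.960 (nominal 0.05) or 2.241 (nominal 0.025). Example, k = 6 and ICC 0.05: m = 10, DE = 1 + 9 × 0.05 = 1.45, √DE = 1.204, error = 2 × [1 − Φ(1.960/1.204)] = 10.4%.

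| Therapists per arm | ICC 0 | ICC 0.02 | ICC 0.05 | ICC 0.10 |
|---|---|---|---|---|
| 3, nominal 0.05 | 5.0% | 9.5% | 16.1% | 25.0% |
| 4, nominal 0.05 | 5.0% | 8.3% | 13.3% | 20.6% |
| 6, nominal 0.05 | 5.0% | 7.1% | 10.4% | 15.5% |
| 10, nominal 0.05 | 5.0% | 6.2% | 8.0% | 11.0% |
| 3, nominal 0.025 | 2.5% | 5.6% | 10.9% | 18.8% |
| 4, nominal 0.025 | 2.5% | 4.8% | 8.6% | 14.8% |
| 6, nominal 0.025 | 2.5% | 3.9% | 6.3% | 10.4% |
| 10, nominal 0.025 | 2.5% | 3.3% | 4.5% | 6.7% |

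Simulated null trials (40,000 per setting, unadjusted t-test on change) agree to within about half a percentage point. For example, k = 6 with ICC 0.05 gives 10.2% and 6.0%. A t-test on therapist means, with 2(k − 1) degrees of freedom, stayed at 4.6% to 5.3% at nominal 0.05 in every setting.

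**Step 3: which therapist term is needed.** Write therapist j's contribution as a_j + b_j × time. In a patient's change from baseline a_j cancels and b_j remains. The interaction test is therefore affected by the variance of b_j, and a therapist intercept alone cannot repair it. In simulated pre/post data with 4 therapists per arm who differed in change, the interaction standard error was 0.266 with no therapist term, 0.266 with a therapist intercept, and 0.389 with therapist by time.

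**Step 4: power of a model that counts therapists.** Noncentrality is 2.739/√DE, with a t reference on 2(k − 1) degrees of freedom, alpha 0.05 and 60 per arm.

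| Therapists per arm | ICC 0.02 | ICC 0.05 |
|---|---|---|
| 3 | 43% | 33% |
| 4 | 53% | 42% |
| 6 | 62% | 54% |
| 10 | 70% | 64% |

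The comparison is 78% under independence. At alpha 0.025 with 4 per arm, the figures are 38% and 29%, against 69% under independence.

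**The case against.** **Inflation is not demonstrated.** Correct. A reader might infer that the trial's standard errors are too small and its error rate is exceeded. The documents do not support that as a fact: they give no ICC and no number of therapists, and at ICC 0 the planned test holds its level. With 10 therapists per arm and ICC 0.02 the error is only about 6%.

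**Therapist variation is actively limited.** Both therapies are manualised, with certification on six practice sessions, weekly supervision, drift correction and blinded fidelity rating. This is a fair reason to expect a small ICC, but not to assume zero. The plan itself provides for therapists falling below standard, and concedes that sessions may go unrecorded under COVID-19 precautions.

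**Nesting is inferred.** Also correct. The separate providers, supervisors and assigned treatments point strongly to it, but no sentence rules out a therapist who delivers both.

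**Mixed models can handle correlation.** The plan mentions their flexibility in modelling correlation as a general advantage. It specifies no therapist level.

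**Inference could be confined to these therapists.** This is a legitimate choice of target, under which the therapists are taken as given. But the hypothesis is worded as CPT against IDC in this population, and the plan does not state the narrower target.

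**A therapist-level primary test could sink the trial.** This stands. Step 4 shows how much power is lost when therapists are few, which is why the model belongs beside the primary analysis and need not replace it.

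**Conclusion.** The concern holds conditionally. The plan strongly implies several therapists nested within arm, and neither the analysis nor the sample size allows for them. If therapists differ in their patients' change, the interaction standard error is too small and the type I error exceeds nominal: about 6% to 25% at 0.05 and 3% to 19% at 0.025. Those ranges rest on assumed values (60 analysed per arm, equal caseloads, ICC 0.02 to 0.10, 3 to 10 therapists per arm). The ICC and the number of therapists cannot be narrowed from the documents. The omission does not invalidate the primary analysis, but as planned a reader could not tell a CPT effect from a therapist effect.

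**What to change.** 1. Record therapist ID for every patient, including any change of therapist.
2. State how many therapists deliver each arm and whether any deliver both, and reconcile the two descriptions of the IDC providers (research staff in the Methods overview, licensed provider under Potential Risks).
3. Prespecify, and report beside the primary analysis, the same mixed model with a therapist-within-arm random effect on change: a random slope if time is linear, a therapist-by-visit effect if time is categorical. An intercept alone is not enough. Use Satterthwaite or Kenward-Roger degrees of freedom.
4. Say in advance that a CPT effect which does not survive this model will be described as not robust to therapist differences. Report the estimated therapist variance with it. A zero estimate is not proof of no variation: in simulations at ICC 0.02 the estimate was zero in 40% to 46% of trials.
5. If an arm turns out to have one therapist, state as a limitation that no model can separate therapist from treatment.

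The cost is one recorded variable and one additional model. The additional model will give a wider interval and, when therapists are few, much lower power (about 42% to 53% at 4 per arm for ICC 0.05 to 0.02). Its result should be read with that in mind. The primary analysis and the sample size need not change.
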